**1.0 Objectives / Specific Aims**

The objective of this project is to develop and test a method of providing real-time augmentation of hip proprioceptive feedback during post-stroke walking. Our central hypothesis is that augmented proprioception will increase the mechanics-dependent modulation of step width, an important gait stabilization strategy. The first aim of this study is to identify the physiological mechanism underlying the beneficial effects of sensory augmentation on step-by-step gait stabilization. Here, we will differentiate between the potential mechanisms of altered perception and cutaneous cueing. The second aim is to determine whether personalizing sensory augmentation methods to individual participants produces greater beneficial effects on post-stroke gait stability. Here, we will identify the optimal combination of vibration pattern and location for each participant, and test whether this personalized stimulation is superior to standard methods. The third aim is to establish the safety, feasibility, and efficacy of a rehabilitation intervention centered on repeated exposure to sensory augmentation during gait. This will be accomplished through a small-scale clinical trial.

**2.0 Background**

Chronic stroke survivors often experience gait instability, which can reduce quality of life through an increased fall-risk and fear of falling [1-5]. Unfortunately, recent clinical trials focused on strengthening and balance [6], multifactorial fall prevention [7], and locomotor training [8] have all failed to substantially impact this important problem, likely because they were not targeted to the specific mechanisms underlying post-stroke instability. To overcome this obstacle, we must design interventions based on a mechanistic understanding of gait instability, which can ultimately be accessed by patients outside of cutting-edge research laboratories

As it is unlikely that a single intervention will “cure” post-stroke gait instability, our long-term goal is to develop a toolbox of interventions, from which clinicians can select the most appropriate option for individual patients. Toward this goal, this study will investigate the real-time augmentation of hip proprioceptive feedback during post-stroke walking. Essentially, sensory stimulation will augment perceived movement errors, a direct extension of methods promoting useful gait adaptation by mechanically augmenting movement errors [9-10].

This proposal is based on our prior work revealing a sensorimotor strategy of sensing the body’s mechanical state using hip proprioceptive feedback [11] and actively adjusting foot placement in response [12]. This strategy is often disrupted in chronic stroke survivors with poor balance [13]. Our ongoing work indicates that deficits in this stabilization strategy can be improved through mechanical error-augmentation. Here, we will test

whether sensory error-augmentation has similar beneficial effects, while investigating the underlying mechanism and determining whether sensory augmentation should be personalized to individual patients.

### 3.0 Intervention to be studied

In this study, Aims 1 and 2 do not involve an intervention, instead including cross-sectional mechanistic experiments. Aim 3 will test the safety, feasibility, and efficacy of a novel intervention involving low-intensity vibration applied over the bilateral hip abductor muscles of chronic stroke survivors during walking. This Aim will take the form of an early-stage, small-scale (n=44 participants) randomized controlled clinical trial.

The precise intervention to be studied is novel, as the vibration amplitude applied during walking will be directly controlled by the user's walking mechanics, allowing us to augment the sensory information available to users. However, the method and form of the vibration itself is not novel. Many prior studies have used vibrating motors (as in the present study) to deliver the same type of mechanical vibration to clinical populations during the performance of functional movement tasks (e.g. reaching, standing, walking) [14-17]. We ourselves have published work investigating the effects of mechanical vibration [11, 18-19], and have an IRB-approved project that involves these methods (Pro00046775).

No medication is involved in the intervention, and FDA approval will not be required for the use of our vibrating tactors, which deliver minimal mechanical energy to users – instead simply evoking a sensory response.

The rationale for the intervention is to use non-invasive methods (vibration) to improve the sensory accuracy of chronic stroke survivors. This low-risk method could have the potential to produce large improvements in patient functional mobility. While we have observed no adverse events in the use of these methods, and no such adverse events have been reported in the literature due to the use of these methods, one of the goals of this project will be to definitively establish the safety of this intervention.

For the intervention, the control group will receive vibration applied over the bilateral hip abductors, just as the experimental group. However, the vibration will not be linked to the user's mechanics, instead being randomly delivered – a method that has been used previously [11].

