### 4.0 Study Endpoints

For the intervention in Aim 3, our outcome measure of safety will be the proportion of participants who experience an adverse event potentially related to the intervention (e.g. skin irritation; falls) or any serious adverse event (e.g. hospitalization; death). Our primary measures of feasibility will be participant adherence (percentage of training sessions attended) and drop-out (non-attendance of final assessment session). We will also track the total walking time across training sessions (of a maximum possible 312 minutes). Our primary measure of efficacy will be changes in  $\rho_{\text{disp}}$ , a metric that quantifies the extent to which participants effectively stabilize their gait by adjusting their step width to account for pelvis dynamics [20]. Our secondary measures of efficacy will be the common clinical measures of Functional Gait Assessment score, Activities-specific Balance Confidence score, overground gait speed, and fear of falling.

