## 10.0 Study Design / Methods

A total of 120 chronic stroke survivors will be recruited for an initial Screening session to determine eligibility for enrollment in the subsequent Aims. From this initial session, 40 stroke survivors will be recruited for Aim 1, and a separate 40 stroke survivors will be recruited for Aim 2. From these 80 participants in Aims 1 and 2, a total of 44 will be recruited for Aim 3. Aim 1 involves a single-session experiment, Aim 2 involves two experimental sessions, while Aim 3 involves an intervention with a total of 10-11 sessions. Participants will be enrolled in this study for a period of a year, allowing time to complete all potential sessions.

In the initial Screening session, participants will walk on an instrumented treadmill for 2-minutes. We will calculate  $\rho_{\text{disp}}$  (a measure of the typical gait stabilization strategy) using LED markers and inertial measurement units placed over participants' legs and pelvis. If  $\rho_{\text{disp}}$  is less than 0.56 (well below control norms), participants will qualify to progress to the subsequent Aims. During the Screening session, we will also quantify the secondary

measures of: Functional Gait Assessment; Activities-specific Balance Confidence scale, Fugl-Meyer Lower Extremity Motor Function subscale; Fugl-Meyer Lower Extremity Sensation subscale; self-selected and fastest-comfortable overground gait speed; fear of falling; fall history. All of these secondary measures are commonly used in clinical practice.

In Aim 1, participants will complete a single-session experiment. We will quantify the cutaneous detection threshold for vibration delivered over the bilateral hip abductors. We will also calculate the lateral sway evoked by vibration of each leg, quantified as the shift in center of pressure while standing on a force plate. Participants will then perform a series of treadmill walking trials. In some of these trials, vibration will be applied to the hip abductors or lateral trunk, while we quantify  $\rho_{\text{disp}}$ .

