## 11.0 Data Management

For Aim 1, our first analysis will be correlation-based, testing whether metrics of altered perception or cutaneous cueing are associated with the beneficial effects of sensory augmentation. For each participant, we will quantify four independent variables: cutaneous detection threshold (paretic and non-paretic legs); lateral sway distance evoked by hip abductor vibration (paretic and non-paretic legs). We will also quantify the effect of sensory augmentation during gait as the mean change in paretic  $\rho_{\text{disp}}$  between the Normal and Vibrated Abductors trials ( $\Delta \rho_{\text{disp}}$ ). We will test whether each of the four independent

variables is significantly associated with  $\Delta \rho_{\text{disp}}$ , using an alpha value of 0.0125 to account for multiple comparisons. Our second analysis will involve a repeated measures experimental design – directly testing whether vibration designed solely to provide cutaneous cues (Vibrated Trunk condition) has a smaller beneficial effect than vibration designed to elicit both cutaneous cues and an altered perception of pelvis mechanics (Vibrated Abductors condition). For this analysis, we will use a repeated measures ANOVA to compare mean paretic  $\rho_{\text{disp}}$  values during the Normal, Vibrated Abductors, and Vibrated Trunk trials.

For Aim 2, our primary statistical analysis will compare the average increase in paretic  $\rho_{\text{disp}}$  values during Standard Augmentation and Personalized Augmentation conditions (relative to Normal). We will use a paired t-test to compare these  $\Delta \rho_{\text{disp}}$  values. Secondarily, we will use a repeated measures ANOVA to test for group-wide effects of vibration pattern and location, based on data from the first session.

For Aim 3, our primary statistical analysis will use an independent t-test to determine whether the change in paretic  $\rho_{\text{disp}}$  differs significantly between the Augmented and Control groups.

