Power analyses were performed for each Aim. For Aim 1, the proposed sample size (n=40) was selected to be able to detect a moderate correlation ( $r=0.5$ ) between our input variables and  $\Delta \rho_{\text{disp}}$ . Aim 2 was powered to detect a moderate effect size (Cohen's  $d = 0.5$ ) between Standard and Personalized sensory augmentation methods. For our Aim 3 intervention, we estimate an effect size of 1.0 based on our prior results. It should be noted that we expect this effect to increase with the repeated exposure to sensory augmentation proposed here. With an effect size of 1.0 and an alpha value of 0.05, we will need 17 participants per group for 0.80 power. We propose 22 participants per group to account for 20% dropout.

Steps will be taken to minimize the risk of loss of confidentiality. All data will be stored on a password-protected computer and password-protected secure server that is backed-up nightly.

The RESTORE registry (Pro#00037803), from which this study will recruit subjects, also serves as a data analysis tool by which interdisciplinary teams may share data across projects and provide MUSC's stroke recovery research community with a more complete registry with key stroke elements. Some subjects may have participated or will participate in other stroke related research studies at MUSC. Sharing data from this and other stroke research studies with RESTORE will allow for more targeted recruitment efforts in the future and could reduce the burden placed on subjects by reducing the duplicative efforts of collecting common data and physical function assessments requested by multiple studies and storing them in one centralized and secure location.

Subjects are informed in the consent process if they enroll into the RESTORE registry, their data from this study will be shared. Subjects will be asked to sign a HIPAA authorization stating their health information may be disclosed to MUSC investigators requiring their data for their research projects upon approval by an Institutional Review Board.

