## 12.0 Provisions to Monitor the Data to Ensure the Safety of Subjects

A Data Safety Monitoring Board (DSMB) will oversee the experiments in Aim 3 (a small-scale randomized controlled trial). This board will consist of a neurologist, a statistician,

and an experienced rehabilitation researcher (all with no direct ties to this study). On a quarterly basis, the DSMB will review the status of the study. The role of the DSMB will be to:

- Protect the safety of study participants
- Review the research protocol, informed consent documents, amendments, and plans for data safety and monitoring
- Evaluate the progress of the trial, including periodic assessments of data quality and timeliness, recruitment, accrual, and retention, participant risk vs. benefit, and other factors that may potentially affect study outcome
- Review study performance, make recommendations and assist in the resolution of problems reported by the Principal Investigator
- Report to the IRB on the safety and progress of the trial
- Ensure the confidentiality of the study data and the results of the monitoring
- Advise the IRB and the study investigators as to whether the protocol should continue as scheduled or undergo a modification due to a finding from the monitoring process

Any adverse events will be recorded, monitored, and promptly reported to the IRB, following policy HRPP 4.7. Our exclusion criteria will minimize the risk of enrolling participants with severe cardiovascular risk. Scheduled rest breaks will be provided between trials during experimental testing, as well as whenever requested. Minimization of risk of adverse events will be accomplished by monitoring vital signs during trials in which subjects are performing potentially demanding exercise. Collected data and any events potentially affecting participant safety will be reviewed by the principal investigator after each data collection session.

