## **13.0 Withdrawal of Subjects**

Participants will be withdrawn from the study without their consent if study staff determine that the participants are at risk of negative health events (e.g. large increase in blood pressure from the initial screening assessment; consistent inability to maintain balance while walking on the treadmill). If a participant voluntarily withdraws from the study, their results will not be included in our data analysis, as our intervention sample size accounts for 20% dropout.

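### Section 13 excludes voluntary withdrawals from the analysis without exempting the Aim 3 safety proportion; secondarily, Section 3 sets a definitive safety goal that 44 participants can address only as a preliminary estimate

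*Combined protocol and SAP*

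**What the plan says.** **Safety outcome.** For Aim 3, Section 4 states that "our outcome measure of safety will be the proportion of participants who experience an adverse event potentially related to the intervention", or any serious adverse event. Its examples of related events are skin irritation and falls. It gives no acceptable rate, confidence level or analysis set.

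**Withdrawals.** Section 13 first allows staff to withdraw participants whom they judge to be at health risk. It then adds that when someone "voluntarily withdraws from the study, their results will not be included in our data analysis, as our intervention sample size accounts for 20% dropout". That exclusion names voluntary withdrawal only, and is silent on whether it reaches safety.

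**Monitoring.** Section 12 says "Any adverse events will be recorded, monitored, and promptly reported to the IRB", and provides for quarterly DSMB review.

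**Goal.** Section 3 says "one of the goals of this project will be to definitively establish the safety of this intervention", while describing Aim 3 as a small trial at an early stage. Section 1 is more measured: "The third aim is to establish the safety, feasibility, and efficacy of a rehabilitation intervention centered on repeated exposure to sensory augmentation during gait".

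**Size.** Section 11 derives 17 per group from an efficacy effect size of 1.0 and then says "We propose 22 participants per group to account for 20% dropout". No safety precision is stated.

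**The concern.** The safety result of Aim 3 is a proportion, so its meaning depends on who is in the numerator and who is in the denominator. Section 13 is the only text that says whose results are left out of the analysis, and it does not exempt safety. An analyst who follows it as written would remove a participant who stopped because of skin irritation or a fall, together with the event itself. If the choice is left until events and withdrawals are known, it can be made with the result in view.

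The second issue is the gap between goal and design. A report with no events could be read as meeting the goal in Section 3, although the data would still be compatible with event rates that nobody would call definitively excluded.

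**Working it through.** **1. The plan's own sample size.** Inputs from Section 11: effect size 1.0, alpha 0.05, power 0.80, independent t-test, 20% dropout. Sidedness is not stated; two-sided is assumed. The noncentral t calculation gives 16.7, so 17 per group (power 0.807). Dropout inflation gives 17 / 0.8 = 21.25, so 22 per group and 44 in total. The plan's figures reproduce, and they rest on efficacy alone.

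**2. Effect of the withdrawal rule on the safety proportion.** Let x of n participants have an event, and let w leave voluntarily, a of them affected. The full proportion is x/n; the literal reading of Section 13 reports (x − a)/(n − w). The reported value is too low when a/w > x/n and too high when a/w < x/n. Illustrations for one arm of 22, all with assumed counts:

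| Assumed situation | All exposed | Voluntary leavers removed |
|---|---|---|
| 1 affected; that person alone leaves | 1/22 = 4.5% | 0/21 = 0% |
| 1 affected who stays; 4 unaffected leave | 1/22 = 4.5% | 1/18 = 5.6% |
| 2 affected; both among 4 leavers | 2/22 = 9.1% | 0/18 = 0% |

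Four leavers is 4/22 = 18.2%, within the planned 20%. The bias is downward if leaving is related to having an event, and upward if only unaffected people leave.

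**3. What the design can say about safety.** The documents give no confidence level, so 95% is assumed. With zero events the exact upper limit is 1 − 0.025^(1/n) two-sided and 1 − 0.05^(1/n) one-sided.

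| Group | n | Two-sided | One-sided |
|---|---|---|---|
| Augmented arm, Aim 3 | 22 | 15.4% | 12.7% |
| Both Aim 3 arms | 44 | 8.0% | 6.6% |
| Aims 1 and 2 | 80 | 4.5% | 3.7% |

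Only the first row concerns repeated vibration linked to the walker's mechanics; Control vibration is random. The last row lies outside the Section 4 outcome and reflects one or two sessions. It cannot be added to the others as independent people: "From these 80 participants in Aims 1 and 2, a total of 44 will be recruited for Aim 3".

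At an illustrative true rate of 5%, the chance of seeing no event is 0.95^22 = 32% in one arm and 0.95^44 = 10% in both.

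Zero events may not be the likely outcome, because the composite counts mild skin irritation, which Section 14 names as a risk. With events, the exact two-sided intervals are 0.1% to 22.8% for 1/22 and 1.1% to 29.2% for 2/22.

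**The case against.** The strongest reply is that Section 13 was meant for efficacy only. It justifies the exclusion by the dropout allowance, which Section 11 derives for the efficacy test. Section 4 makes drop-out a primary feasibility measure, which could not be counted properly if voluntary leavers were removed from every analysis. Section 12 requires adverse events to be recorded whatever happens later. This reading is plausible and may well be the intended one. What remains is that no section states it, and that recording an event or reporting it to the IRB does not settle who is counted in the Section 4 proportion.

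A reader might infer that the rule always makes the intervention look safer. The documents do not support that: the exclusion applies whatever the reason for leaving, so the direction can go either way. Nor does it cover participants withdrawn by staff for health risk, so one likely route for safety-related exits is unaffected.

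On the goal, the fair reply is that the claim of definitiveness is one word in a rationale paragraph. No safety hypothesis, threshold or decision depends on it, and Section 15 anticipates larger studies. This stands, and is why the point is secondary. A reader might also infer that the trial is too small, or that 8% or 15% is unacceptable. The documents give no tolerable rate, the composite includes mild irritation, and sizing an early trial on efficacy is not an error.

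**Conclusion.** The main point holds as a minor ambiguity with a real consequence. As written, Section 13 permits voluntary leavers to be dropped from the Aim 3 safety proportion, and nothing elsewhere rules this out. In an arm of 22, a single event can be reported as 0% or as 5.6% instead of 4.5%, depending on who leaves; these counts are assumed, since the documents give no event rate. It cannot be said that the sponsor intends to exclude safety data, nor that the bias would certainly be downward.

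The secondary point also holds. At an assumed 95% level, even an event-free Aim 3 leaves two-sided upper limits of 15.4% for the Augmented arm and 8.0% pooled, and an event-free Aims 1 and 2 would leave 4.5%. That supports a preliminary safety statement, not a definitive one. The mismatch is confined to Section 3. Section 1 does not claim definitiveness and, read with its own reference to a small-scale trial, needs no change.

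**What to change.** 1. **Section 13:** state that the exclusion of voluntary withdrawals does not apply to safety, and that every Aim 3 participant exposed to vibration, including all withdrawals of either kind, stays in the safety numerator and denominator. This matters most, and should be settled before events and withdrawals are known.
2. **Section 3:** replace the definitive goal with a preliminary assessment of safety.
3. **Section 11:** add that the Section 4 safety proportion will be reported with exact 95% intervals per arm and pooled, with related non-serious events and serious events shown separately.

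The cost is one sentence each in Sections 13 and 11 and a change of wording in Section 3. No new data collection and no change in sample size are needed. The downside is a weaker safety claim.

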### 4.0 Study Endpoints

For the intervention in Aim 3, our outcome measure of safety will be the proportion of participants who experience an adverse event potentially related to the intervention (e.g. skin irritation; falls) or any serious adverse event (e.g. hospitalization; death). Our primary measures of feasibility will be participant adherence (percentage of training sessions attended) and drop-out (non-attendance of final assessment session). We will also track the total walking time across training sessions (of a maximum possible 312 minutes). Our primary measure of efficacy will be changes in  $\rho_{\text{disp}}$ , a metric that quantifies the extent to which participants effectively stabilize their gait by adjusting their step width to account for pelvis dynamics [20]. Our secondary measures of efficacy will be the common clinical measures of Functional Gait Assessment score, Activities-specific Balance Confidence score, overground gait speed, and fear of falling.

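### Aim 3 gives no way of learning of adverse events in participants who stop attending, and no window or denominator for its safety proportion, which may therefore omit events among about 9 of 44

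*Combined protocol and SAP*

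**What the plan says.** Section 4.0 (Study Endpoints) defines the Aim 3 safety outcome as a proportion of participants. A participant counts if they have an adverse event possibly related to the intervention, with skin irritation and falls as examples, or "any serious adverse event (e.g. hospitalization; death". The section does not say over what period events count or who forms the denominator. Its feasibility measures include "drop-out (non-attendance of final assessment session".

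Section 12.0 states: "Any adverse events will be recorded, monitored, and promptly reported to the IRB", under a named institutional policy. On timing it says: "Collected data and any events potentially affecting participant safety will be reviewed by the principal investigator after each data collection session". A data safety monitoring board reviews the trial quarterly, including retention and the balance of risk and benefit.

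Section 13.0 (Withdrawal of Subjects) leaves the results of anyone who withdraws voluntarily out of the data analysis, on the ground that the sample size already allows for 20% drop-out. It makes no exception for safety data. It also lets staff withdraw people judged to be at risk of a health event.

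Section 3.0 describes Aim 3 as a "small-scale (n=44 participants) randomized controlled clinical trial" and names establishing the safety of the intervention as one of the project's goals. Section 11.0 sets the drop-out allowance: "We propose 22 participants per group to account for 20% dropout".

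**The concern.** The plan's own examples of serious events, hospitalization and death, happen outside the laboratory and can themselves end attendance. The people whose safety status is hardest to learn may therefore be those most likely to have had an event. Section 13.0 points the same way, since staff may withdraw a person because of a health risk.

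Falls raise a related problem. Section 10.0 puts participants in a harness for treadmill and overground walking trials, so most falls that could count would occur between sessions. Fall history is taken at Screening but is not in the list of Aim 3 pre and post assessments. No described procedure asks about falls at home, even among people who attend.

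Safety is one of the three stated purposes of Aim 3. An event that nobody asked about cannot be recovered at analysis, and the monitoring board would see the same incomplete count.

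**Working it through.** **Does each described procedure reach someone who has stopped attending?**

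- Skin check (sections 10.0 and 14.0): done after sessions, so no.
- Vital signs (section 12.0): taken during demanding trials, so no.
- Principal investigator's review (section 12.0): follows each data collection session and covers what is already known.
- Recording and reporting to the IRB (section 12.0): not limited to attenders, but it applies once an event is known and gives no route to knowing.
- Quarterly board review (section 12.0): sees retention figures and reported events. It is not said to trace the status of people who left.

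No section describes contact with a person who misses a session or leaves.

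**Inputs.** 44 randomised, 22 per group (sections 3.0 and 11.0). Drop-out allowance 20% (section 11.0), taken here to mean drop-out as defined in section 4.0. The documents give no adverse event rates.

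**Step 1: reproduce the plan's figure.** Section 11.0 says: "With an effect size of 1.0 and an alpha value of 0.05", "we will need 17 participants per group for 0.80 power". Sidedness is not stated, so I assume a two-sided test. The two-sample t-test then needs 16.7, so 17 per group, with power 0.807. Allowing for drop-out, 17 / (1 − 0.20) = 21.25, so 22 per group and 2 × 22 = 44. The plan's figures reproduce.

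**Step 2: people affected.** 0.20 × 44 = 8.8, about 9, which leaves 44 − 9 = 35. If exactly 17 per group complete, 44 − 34 = 10 are affected.

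**Step 3: bounds.** With x participants seen to have an event and u of unknown status, the proportion among all 44 lies between x/44 and (x + u)/44.

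| Seen (x) | Unknown (u) | Lower | Upper |
|---|---|---|---|
| 0 | 9 | 0% | 9/44 = 20.5% |
| 0 | 10 | 0% | 10/44 = 22.7% |
| 2 | 9 | 2/44 = 4.5% | 11/44 = 25.0% |

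The counts of 0 and 2 are hypothetical. Each person of unknown status adds 1/44 = 2.3 percentage points to the upper limit.

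**Step 4: the missing denominator.** Two participants with events among 35 completers could be reported as 2/35 = 5.7% or as 2/44 = 4.5%. The plan does not say which.

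**Step 5: comparison with sampling error.** With zero events in n people, the one-sided 95% upper limit is 1 − 0.05^(1/n). For n = 44 it is 6.6%, and for n = 35 it is 8.2%. The second figure describes all 44 only if those who left carry the same risk as those who stayed. Without that assumption, unknown status can matter more than sampling error.

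**Direction.** On a denominator of 44, unseen events lower the numerator. On a completer denominator, the proportion is too low if people who leave have more events than people who stay. Both point downward, but the second depends on that condition.

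**The case against.** The strongest reply is that section 12.0 commits to recording any adverse event, without limiting this to sessions or attenders, and cites an institutional policy. Neither that policy nor the consent form is in the text reviewed, and either might tell participants to report problems. The skin check addresses one local risk, and the investigator's review need not define when events are sought. An investigator stands near participants in all walking trials, so an event there that ends participation would be seen. Staff know whom they themselves withdraw, they hold contact details, and the board sees retention every quarter. Call schedules may also sit in an operations manual. Finally, 20% is a sample-size allowance, and someone who misses only the final assessment may have been observed at every training session.

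Much of this stands. A reader might infer that events are sought only at attended sessions, or that a non-attender's event would come to light only by chance. The documents support neither: they are silent on the route and do not restrict it. The reply also shows that the nine would not all be wholly unknown.

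It does not supply what is missing. A duty to record is not a means of finding out, and no section gives the window or the denominator. Section 13.0, read literally, could remove even an event that was found. It may have been meant for efficacy results only, but it does not say so.

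**Conclusion.** The point holds as a gap in ascertainment and definition. Followed as written, the plan can produce a safety proportion that omits events among participants who stop attending, and the likely direction is downward. The group at issue is about 9 of 44 at the plan's own allowance. With zero events seen in the other 35, the range is 0% to 20.5%. That upper end requires every one of the nine to have had an unseen qualifying event. It is an outer bound, because no event rates are given and some drop-outs will have been observed for most sessions. Any single figure for the bias would rest on an invented rate.

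Two limits apply. A reader might infer that drop-out is overstated as a feasibility failure when a serious event is its cause. It is not: section 4.0 counts non-attendance whatever the reason, and finding the event would leave that count unchanged. And the section 13.0 exclusion names voluntary withdrawal only, so it does not by its terms cover death or withdrawal by staff. The sample size is unaffected.

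**What to change.** 1. **Sections 4.0 and 12.0, ascertainment.** Ask every randomised Aim 3 participant a fixed set of questions on adverse events, falls and hospitalization at each visit. If the final assessment is missed, ask them by phone on its planned date, whatever the person's attendance or withdrawal status, unless they refuse contact.
2. **Section 4.0, definition.** Use all randomised participants as the safety denominator and count events from randomisation to the planned final assessment date. Report how many have unknown status, with best-case and worst-case bounds as in step 3 above.
3. **Section 13.0.** State that the exclusion of voluntary withdrawals does not apply to safety data. Without this, events found by phone could still be left out.

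The cost is a short protocol amendment, a few questions per visit and about nine brief calls by staff who already screen by phone. Some people will decline contact, so some unknown status will remain; the bounds make it visible.
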